5.1.5.2 Toxicities during Maintenance Treatment

Table 12 provides guidelines for management of toxicities that occur during maintenance treatment.

Table 12 Guidelines for Management of Toxicities That Occur during Maintenance Treatment

Event	Action To Be Taken
Hematologic toxicity: Grade 3 or 4	For all patients: 
• Atezolizumab may be continued at the discretion of the investigator.• Withhold obinutuzumab and lenalidomide.• Administer G-CSF for neutropenia per institutional guidelines.• Administer RBCs or platelets as required.• If there is improvement to Grade ≤ 2, resume obinutuzumab and lenalidomide at same dose.• If study treatment is withheld for > 42 days, permanently discontinue study treatment.
Non-hematologic toxicity: Grade ≥ 2	For atezolizumab-related toxicities with possible immune etiology: 
• Follow guidelines presented in Table 11 for the management of atezolizumab-related toxicities with possible immune etiology (i.e., autoimmune colitis, hepatitis, pancreatitis, hypothyroidism, pneumopathy, skin, toxicity, or ocular toxicity). For all other non-hematologic toxicities: 
• Withhold study treatment.• If there is improvement to Grade ≤ 1 or baseline, administer study treatment at full dose.• If study treatment is withheld for > 42 days, permanently discontinue study treatment.

G-CSF = granulocyte colony-stimulating factor.

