4.6.2 Study Treatment Discontinuation

Study treatment should be permanently discontinued in patients who experience any of the following:

- Anaphylaxis, acute respiratory distress, or Grade 4 IRR
 - If a Grade 3 IRR is recurrent during the second and subsequent cycles, study treatment may be discontinued at the discretion of the investigator, following an individual benefit-risk assessment.
- Life-threatening adverse event
- Grade ≥ 3 non-immune-mediated adverse event that is considered to be related to study treatment and does not resolve to Grade ≤ 2 within 21 days

- Non-immune-*mediated* adverse event that is considered to be treatment related and requires study treatment to be withheld for >21 days
- Immune-*mediated* adverse event that requires atezolizumab to be withheld for >42 days, unless approved by the Medical Monitor
- Any adverse event that meets criteria for permanent discontinuation per guidelines provided in Section 5.1
- Disease progression

Because of the potential for tumor flares with immunotherapies, resulting in early apparent radiographic progression (pseudoprogression/tumor immune infiltration), including the appearance of new lesions followed by delayed response (Wolchok et al. 2009), patients whose CT scans at the end of Cycle 2 meet criteria for disease progression may continue to receive study treatment at the discretion of the investigator and following discussion with the Medical Monitor, if certain criteria are met (see Section 3.1.4 for details). Cases of delayed pseudoprogression have also been described in patients with solid tumors treated with immunotherapies. In case of CT- findings suggestive for pseudoprogression in patients with persistent clinical benefit, the investigator should contact the Medical Monitor to discuss further patient management. Patients who continue to receive study treatment should have a CT scan repeated 4–8 weeks later.

- Pregnancy

In case of toxicity solely attributable to one drug of the combination requiring discontinuation, the other two drugs may be continued for patients experiencing clinical benefit as determined by the investigator after discussion with the Medical Monitor.

The primary reason for study treatment discontinuation should be documented on the appropriate eCRF.

Patients who discontinue study treatment will not be replaced, except as outlined below:

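### For a related, non-immune Grade 3–4 cytopenia in maintenance, Section 4.6.2 stops treatment after 21 days while Table 12 allows a same-dose restart up to 42 days; Table 12 also omits Table 10's bleeding stop

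*Combined protocol and SAP*

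**What the plan says.** Section 4.6.2 lists events after which study treatment should be permanently discontinued; meeting any one is enough. One bullet covers non-immune-mediated events of Grade 3 or higher that are "considered to be related to study treatment and does not resolve to Grade ≤ 2 within 21 days". The next covers a non-immune-mediated "adverse event that is considered to be treatment related and requires study treatment to be withheld for >21 days". Neither names a treatment phase. A separate bullet adds "Any adverse event that meets criteria for permanent discontinuation per guidelines provided in Section 5.1". The list also includes any life-threatening adverse event.

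Table 12 (Section 5.1.5.2) governs maintenance. For Grade 3–4 hematologic toxicity it withholds obinutuzumab and lenalidomide in all patients, then says "If there is improvement to Grade ≤ 2, resume obinutuzumab and lenalidomide at same dose". Its limit is: "If study treatment is withheld for > 42 days, permanently discontinue study treatment". The non-hematologic row carries the same 42-day limit and, for toxicities without a possible immune etiology, says "If there is improvement to Grade ≤ 1 or baseline, administer study treatment at full dose".

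Table 10 (Section 5.1.5.1) governs hematologic toxicity in induction only. It permanently stops study treatment for Grade 3–4 thrombocytopenia with bleeding that the investigator judges significant. For patients on thromboprophylaxis whose platelets fall below 20,000/µL, it tells sites to reduce LMWH or consider pausing platelet inhibitors. Table 12 contains neither instruction.

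**The concern.** A site with a maintenance patient whose related Grade 3–4 cytopenia takes more than three weeks to recover cannot follow both rules. One ends treatment for good; the other restarts two drugs at the same dose. Sites that each follow the protocol could therefore make opposite irreversible decisions for the same event. Maintenance exposure, and the incidence of discontinuation for reasons other than progression tabulated under Section 6.3, would then depend partly on which section a site read.

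The bleeding gap is a safety matter. Under Section 4.3.2.6, all patients take low-dose aspirin during lenalidomide treatment and until 28 days after the last dose, so a lenalidomide hold does not promptly end aspirin. A patient with severe thrombocytopenia and significant but not life-threatening bleeding has a listed permanent stop in induction. In maintenance, the table's only specific instruction is to resume on recovery.

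**Working it through.** The plan states no figure to reproduce. The check compares the rules by recovery day and then compares the stop lists.

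**Inputs.** Section 4.6.2: 21 days to Grade ≤2, or a hold of more than 21 days. Table 12: restart at Grade ≤2, permanent stop after a hold of more than 42 days. Assumption: the event is related and non-immune-mediated, and withholding starts at onset.

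| Recovery to Grade ≤2 | Section 4.6.2 | Table 12 | Agree? |
|---|---|---|---|
| By day 21 | No 21-day stop | Restart, same dose | Yes |
| Days 22–42 | Permanent stop | Restart, same dose | No |
| Still held after day 42 | Permanent stop | Permanent stop | Yes |

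Length of the conflict: 42 − 21 = 21 days. Ratio of the limits: 42 / 21 = 2.

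**How exact the window is.** The first 21-day bullet counts days to resolution; Table 12 counts days withheld. If the hold starts k days after onset, the lower end stays at day 22 from onset and the upper end moves to day 42 + k. The second bullet counts days withheld, as Table 12 does. But it refers to study treatment, which Section 2 defines as the combination of all components, and Table 12 says of the third drug "Atezolizumab may be continued at the discretion of the investigator". If atezolizumab continues, the second bullet may not be met; the first still is. So days 22–42 is approximate, and the conflict rests mainly on the first bullet.

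**Can other text reconcile the rules?**
- Section 5.1.5 takes maximum delays from the tables. It does not say the tables override Section 4.6.2.
- Table 11, for induction, repeats the 21-day bullets, which fits 21 days for induction and 42 for maintenance. Section 4.6.2 does not say so.
- The Section 4.6.2 bullet pointing to Section 5.1 adds criteria to the list and relaxes none.
- Section 4.6.2 does use 42 days, but only for immune-mediated events. A careful reader could take 21 days as deliberate for the rest.
- Its continuation clause, which begins "In case of toxicity solely attributable to one drug of the combination requiring discontinuation", lets the other two drugs go on. It does not permit the causative drug to restart, whereas Table 12 restarts both withheld drugs.

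**Bleeding stop.**

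| Thrombocytopenia Grade 3–4 with significant bleeding | Induction | Maintenance |
|---|---|---|
| Specific permanent stop | Yes, Table 10 | None in Table 12 |
| Life-threatening bleed | Stop, Section 4.6.2 | Stop, Section 4.6.2 |
| Not life-threatening | Stop, Table 10 | Unacceptable toxicity (Section 4.3.2.5) or withdrawal (Section 4.6.1) |
| Platelets <20,000/µL: LMWH and platelet inhibitors | Table 10 | No counterpart in Table 12 |

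A Grade ≥2 bleed recorded as its own event also enters Table 12's non-hematologic row, but that row too ends in a full-dose restart on recovery to Grade ≤1 or baseline.

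**The case against.** The best defense is that the specific rule governs. Section 5.1.5 sends the reader to the tables for maximum delays and assigns maintenance to Section 5.1.5.2. Table 10 also departs from Section 4.6.2 within induction: after a hold of more than 21 days it stops lenalidomide but allows obinutuzumab to continue with Medical Monitor discussion. The tables therefore look like event-specific rules throughout. This is good evidence of intent, and it decides the direction of the fix. It does not settle the text, because Section 4.6.2 is written as a mandatory list with no maintenance exception.

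On exposure, obinutuzumab is given every 2 months in maintenance and lenalidomide for at most 12 months, so a hold within 42 days may miss no obinutuzumab dose. That is true of the hold itself. The disagreement is about whether the remaining maintenance is given at all.

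On bleeding, a simpler table at the 10 mg maintenance dose is a defensible choice, and Sections 4.4.1 and 5.1.1.4 warn of bleeding risk with anticoagulants and platelet inhibitors in any phase. A reader might infer that a fixed stop in induction becomes a judgment call in maintenance. The documents do not support that contrast: Table 10's criterion is itself left to investigator judgment, and the life-threatening-event stop in Section 4.6.2 is a listed criterion in both phases. What remains is the missing specific stop for bleeding that is not life-threatening.

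**Conclusion.** The conflict is real and should be corrected. For a related, non-immune-mediated Grade 3–4 cytopenia in maintenance, recovery on about days 22–42 leads to opposite instructions, assuming the hold starts at onset. The likely intent is 42 days, but no precedence is stated. The absence of a bleeding stop in Table 12 is a separate, smaller gap, confined to bleeding that is not life-threatening. CR at EOI and the RP2D are unaffected, and Section 6.3 is descriptive.

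Two stronger readings should be resisted. First, because scheduled maintenance hematology is monthly, a reader might infer that the conflict window will be reached routinely. Sections 5.1.1.3 and 5.1.1.4 require closer monitoring after neutropenia or thrombocytopenia, which may show earlier recovery. The documents also give no maintenance cytopenia rate, so no patient count can be offered. Second, a reader might see a further defect in Table 12 letting atezolizumab continue while its 42-day rule stops study treatment as a whole. This is a minor wording ambiguity: the continuation clause in Section 4.6.2 turns on attribution to one drug, not on how many drugs were held.

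**What to change.** 1. In Section 4.6.2, limit the two 21-day bullets to induction and add: For maintenance, see Table 12 (42 days). This also removes the same conflict from Table 12's non-hematologic row.
2. In Table 12's hematologic row, add a permanent stop of obinutuzumab and lenalidomide for Grade 3–4 thrombocytopenia with bleeding that the investigator judges significant, and state that it takes precedence over the same-dose restart. For platelets below 20,000/µL, refer to Table 10's instruction on LMWH and platelet inhibitors.

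Leave the maintenance dose levels as they are. No new data are needed. The changes require IRB/EC approval and, where applicable, regulatory approval, but can go into the next amendment rather than one of their own. The bleeding stop may slightly increase maintenance discontinuations.

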
G-CSF = granulocyte colony-stimulating factor; LMWH = low-molecular-weight heparin.

^a Dose modifications apply only to events that are considered to be related to lenalidomide.

^b If cytopenia is thought to be caused mainly by non-Hodgkin's lymphoma infiltration of the bone marrow, the investigator may decide not to reduce the dose of lenalidomide.

^c For Grade 3 neutropenia, only if sustained (≥ 7 days) Grade 3 or \geq Grade 3 associated with fever (temperature $\geq 38.5^\circ\text{C}$).

Non-Hematologic Toxicities during Induction Treatment

[Table 11](#) provides guidelines for management of non-hematologic toxicities that occur during induction treatment.

Toxicities associated or possibly associated with atezolizumab treatment should be managed according to standard medical practice. Additional tests, such as autoimmune serology or biopsies, should be used to evaluate for a possible immunogenic etiology. For detailed information regarding management of adverse events associated with atezolizumab, please refer to the [Appendix 10](#).

Table 11 Guidelines for Management of Non-Hematologic Toxicities

Event	Action to Be Taken
General guidance for treatment delays and discontinuation	
 • If toxicity occurs before Cycle 1 Day 8 or Cycle 1 Day 15, these doses of obinutuzumab will not be skipped but given after resolution of toxicity. • When a treatment cycle is delayed because of a toxicity resulting from any component of the regimen, all study treatment should generally be held and resumed together to remain synchronized. • If it is anticipated that atezolizumab will be delayed by >21 days, obinutuzumab and lenalidomide should be given without atezolizumab if there is no contraindication. • If one drug is discontinued, treatment with the other two drugs may be continued for patients experiencing clinical benefit as determined by the investigator after discussion with the Medical Monitor. • Permanently discontinue study treatment if any of the following events occur: 
 – Grade ≥ 3 non-immune-mediated adverse event that is considered to be related to study treatment and does not resolve to Grade ≤ 2 within 21 days – Non-immune-mediated adverse event that is considered to be treatment related and requires study treatment to be withheld for >21 days – Immune-mediated adverse event that requires atezolizumab to be withheld for >42 days, unless approved by the Medical Monitor

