IRRs and anaphylaxis	
 • Guidelines for management of IRRs are provided in Sections 4.3.2.1 (obinutuzumab) and 4.3.2.2 (atezolizumab). • Metamizole (dipyrone) is prohibited in treating atezolizumab-associated IRRs because of its potential for causing agranulocytosis. • In case of anaphylaxis, study treatment should be permanently discontinued.
Renal toxicity	
 • Adjust the dose of lenalidomide^a as outlined below: 
 – If creatinine clearance is ≥ 30 but < 60 mL/min, lenalidomide should be given at a dose of 10 mg/day. – If creatinine clearance is < 30 mL/min and dialysis is not required, lenalidomide should be given at a dose of 10 mg every other day. – If creatinine clearance is < 30 mL/min and dialysis is required, lenalidomide should be given at a dose of 5 mg/day. On dialysis days, the dose should be administered after dialysis.

Table 11 Guidelines for Management of Non-Hematologic Toxicities (cont.)

	Event	Action to Be Taken
TLS	Clinical TLS ^b	
 • Withhold study treatment. • Correct electrolyte abnormalities, monitor renal function and fluid balance, and administer supportive care, including dialysis as indicated. Rasburicase therapy (if approved by the local health authority) may be administered as needed to reduce hyperuricemia. • If symptoms resolve completely, resume atezolizumab and obinutuzumab at full dose and resume lenalidomide at a reduced dose^a per guidelines in Section 5.1.5 for current and subsequent cycles. • Perform chemistry panel every other day for the first week after re-initiation of lenalidomide.
	Laboratory TLS ^b	
 • Withhold study treatment. • Correct electrolyte abnormalities, monitor renal function and fluid balance, and administer supportive care as clinically indicated. • If laboratory abnormalities have resolved completely, resume atezolizumab and obinutuzumab at full dose and resume lenalidomide either at current dose or at a reduced dose^a per guidelines in Section 5.1.5 for current and subsequent cycle, at the investigator's discretion.
Peripheral neuropathy	Grade 4 or Myasthenia gravis (any grade) or Guillain-Barre (any grade)	
 • Permanently discontinue study treatment. • Initiate treatment as per institutional guidelines.

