Symptomatic adrenal insufficiency	Grade 2–4	
 • Withhold atezolizumab. • Refer patient to endocrinologist. • Perform appropriate imaging. • Initiate treatment with 1–2 mg/kg/day IV methylprednisolone or equivalent and convert to 1–2 mg/kg/day oral prednisone or equivalent upon improvement. • Resume atezolizumab if event resolves to Grade ≤1 and patient is stable on replacement therapy (if required) within 12 weeks. If corticosteroids have been initiated, they must be tapered over ≥ 1 month to ≤ 10 mg/day oral prednisone or equivalent before atezolizumab can be resumed. Contact Medical Monitor before resuming atezolizumab.
Immune-mediated myocarditis	Grade 3–4	
 • Permanently discontinue study treatment and contact Medical Monitor. • Refer patient to cardiologist. • Initiate treatment as per institutional guidelines and consider antiarrhythmic drugs, temporary pacemaker, ECMO, or VAD as appropriate. • Initiate treatment with 1–2 mg/kg/day IV methylprednisolone or equivalent and convert to 1–2 mg/kg/day oral prednisone or equivalent upon improvement. • If event does not improve within 48 hours after initiating corticosteroids, consider adding an immunosuppressive agent. • If event resolves to Grade 1 or better, taper corticosteroids over ≥ 1 month.

Table 11 Guidelines for Management of Non-Hematologic Toxicities (cont.)

Event		Action to Be Taken
Immune-mediated myocarditis (cont.)	Grade 2	
 Withhold study treatment. Refer patient to cardiologist. Initiate treatment as per institutional guidelines and consider antiarrhythmic drugs, temporary pacemaker, ECMO, or VAD as appropriate. Consider treatment with 1–2 mg/kg/day IV methylprednisolone or equivalent and convert to 1–2 mg/kg/day oral prednisone or equivalent upon improvement. If event resolves to Grade 1 or better, resume study treatment. If corticosteroids have been initiated, they must be tapered over ≥ 1 month to ≤ 10 mg/day oral prednisone or equivalent before atezolizumab can be resumed. Contact Medical Monitor before resuming atezolizumab. If event does not resolve to Grade 1 or better while withholding atezolizumab, permanently discontinue atezolizumab and contact Medical Monitor.
	Grade 1	
 Refer patient to cardiologist. Initiate treatment as per institutional guidelines.

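### Table 12 gives a closed list of immune events for maintenance; read literally, it restarts full dose after four event types that Table 11 stops permanently

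*Combined protocol and SAP*

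**What the plan says.** Section 5.1.5 directs the reader to Section 5.1.5.1 for toxicities in induction and to Section 5.1.5.2 for those in maintenance.

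Table 12 (Section 5.1.5.2) splits non-hematologic toxicities of Grade 2 or higher into two groups:

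- Atezolizumab-related toxicities with possible immune etiology follow Table 11. The instruction specifies them as "i.e., autoimmune colitis, hepatitis, pancreatitis, hypothyroidism, pneumopathy, skin, toxicity, or ocular toxicity".
- All others are withheld. The restart rule is: "If there is improvement to Grade ≤ 1 or baseline, administer study treatment at full dose". Only a hold of more than 42 days leads to the instruction to "permanently discontinue study treatment".

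Table 11 (Section 5.1.5.1) carries no phase limit in its title, but its introduction says that it "provides guidelines for management of non-hematologic toxicities that occur during induction treatment". It permanently stops study treatment in these rows:

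- Peripheral neuropathy: "Grade 4 or Myasthenia gravis (any grade) or Guillain-Barre (any grade").
- Immune-mediated nephritis, Grade 3 or 4.
- Immune-mediated myocarditis, Grade 3–4: "Permanently discontinue study treatment and contact Medical Monitor".

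Section 4.6.2, which is not limited to a phase, permanently stops study treatment for "Life-threatening adverse event" and for "Any adverse event that meets criteria for permanent discontinuation per guidelines provided in Section 5.1".

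**The concern.** In this setting *i.e.* introduces a definition, and the definition leaves out myocarditis, nephritis, Guillain-Barré syndrome and myasthenia gravis. An investigator who follows the maintenance table as worded would place these events in the second group and restart all three drugs at full dose after recovery. Table 11 would never restart them.

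Maintenance is also where most planned atezolizumab is given. Induction has five atezolizumab cycles (Cycles 2–6) and maintenance has up to 24 months of 28 days. For a patient who completes both, 24 of 5 + 24 = 29 dosing periods fall under Table 12.

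What is at stake is patient safety, through wrong re-dosing after a serious immune-mediated event.

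**Working it through.** No formula applies. The check compares the texts and counts events.

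**1. Items in Table 12's list.** Colitis, hepatitis, pancreatitis, hypothyroidism, pneumopathy, skin toxicity (printed with a stray comma, counted once) and ocular toxicity: 7.

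**2. Immune-mediated risks in Section 5.1.2, infusion-related reactions excluded.** Hepatitis, pneumonitis, colitis, pancreatitis, diabetes mellitus, hypothyroidism, hyperthyroidism, adrenal insufficiency, hypophysitis, Guillain-Barré syndrome, myasthenic syndrome or myasthenia gravis, meningoencephalitis, myocarditis, nephritis and myositis: 15.

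**3. Risks covered by the list.** Hepatitis, pneumonitis (as pneumopathy), colitis, pancreatitis and hypothyroidism: 5. Omitted: 15 − 5 = 10.

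**4. Omitted risks where the two tables conflict.** The conditions are a first occurrence, not life-threatening, Grade 2 or higher (where Table 12's row begins), and a hold of 42 days or less.

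| Event | Table 11 | Table 12, read literally |
|---|---|---|
| Immune-mediated myocarditis, Grade 3 | Study treatment stopped permanently | Full dose after recovery |
| Immune-mediated nephritis, Grade 3 | Study treatment stopped permanently | Full dose after recovery |
| Guillain-Barré syndrome, Grade 2–3 | Study treatment stopped permanently (any grade) | Full dose after recovery |
| Myasthenia gravis, Grade 2–3 | Study treatment stopped permanently (any grade) | Full dose after recovery |

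That is 4. The other 10 − 4 = 6 (diabetes mellitus, hyperthyroidism, adrenal insufficiency, hypophysitis, meningoencephalitis, myositis) are not counted, because Table 11 or Appendix 10 also allows resumption after a first event that is not life-threatening.

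**5. Cross-check against all permanent stops.** Unlisted immune-type rows of Table 11 with any permanent stop are neuropathy (with myasthenia gravis and Guillain-Barré), nephritis, myocarditis, suspected HLH/MAS, myositis, hypophysitis and hyperthyroidism: 7 rows, or 8 events if myasthenia gravis and Guillain-Barré are counted separately. Four drop out:

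- HLH/MAS, because Appendix 10 Table 5 itself stops atezolizumab.
- Myositis, stopped only at Grade 4.
- Hypophysitis, stopped at Grade 4, on recurrence, or if it does not resolve to Grade 1 or better while atezolizumab is withheld.
- Hyperthyroidism, stopped only if life-threatening.

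8 − 4 = 4, which agrees with step 4.

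**6. Do other sections settle it?**

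- *Section 4.6.2, life-threatening events.* This does not by itself reach the four events at Grade 2 or 3.
- *Section 4.6.2, Section 5.1 criteria.* Tables 11 and 12 both lie in Section 5.1, so the reader returns to the same conflict.
- *Appendix 10.* It sends myocarditis, neurologic disorders and nephritis to Table 11 with no phase limit. This shows the intent, but Table 11 is introduced as guidance for induction.
- *Section 5.2.3.* All four are adverse events of special interest, reportable within 24 hours. That informs the Sponsor; it does not instruct the site on dosing.

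**The case against.** The strongest reply is that Table 12 selects its rows by sub-heading. The first sub-heading names the broad immune class with no list, and the second covers everything else. Immune-mediated myocarditis plainly belongs to the first class, and the parenthesis appears only in the bullet below. This reading is reasonable and very likely the intended one. But the bullet repeats the sub-heading's phrase and then defines it with a closed list, so the narrower reading is also on the page. The protocol uses *e.g.* elsewhere when it means examples, as in Section 5.2.3, so *i.e.* cannot simply be read that way.

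A second reply is that if Appendix 10 settles HLH/MAS it should settle these four as well. The cases differ: for HLH/MAS Appendix 10 states the stop itself, while for the four it only points to Table 11.

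A third is that Appendix 10 lets atezolizumab be resumed even after permanent-stop criteria are met, so the bar is not absolute. That is true, but it requires full recovery, benefit to the patient, and documented approval by both the investigator and the Medical Monitor, and it concerns atezolizumab only. Table 12's restart row has none of these conditions and applies to all study treatment.

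Last, Grade 4 is not identical to life-threatening: the fallback scale in Section 5.3.4 also includes events needing urgent intervention. This stands as a caution on the boundary of the count. It could widen the conflict but would not remove any of the four.

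What stands overall is that wrong re-dosing is unlikely and that this is a fault of wording.

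**Conclusion.** The concern holds, as a minor point of patient safety. Read literally, Table 12 contradicts Table 11's permanent stop for four event types, under the conditions in step 4 of the check. The count takes Grade 4 events as covered by the life-threatening rule in Section 4.6.2, and excludes HLH/MAS for the reason given. The surrounding text points to stopping, so this is an internal conflict that a careful investigator would probably resolve correctly. It is not a clear instruction to re-dose. The documents give no rate for the four events in maintenance, so no number of affected patients can be stated. No effect on an endpoint, the sample size or an error rate is claimed.

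**What to change.** In Table 12, change *i.e.* to *e.g.*, or replace the parenthesis with a reference to all immune-mediated rows of Table 11 and to Appendix 10. Add a sentence stating that Table 11's permanent-discontinuation criteria for immune-mediated events also apply in maintenance. Remove the stray comma in the skin toxicity item at the same time. The cost is protocol wording only.
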